12.4 Pharmacodynamic/Efficacy Analysis

Haemolysis and Disease related assessments will be listed and summarised at each time point using appropriate descriptive statistics.

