12.0 STATISTICAL METHODS

Statistical programming and analyses will be performed using established statistical methods. Details of all planned analyses will be specified in a separate statistical analysis plan.

The study data will be reported using summary tables, figures, and data listings. Continuous variables will be summarized using mean, standard deviation (SD), coefficient of variation (CV%, as appropriate), median, minimum, maximum, and, as appropriate, geometric mean. Categorical variables will be summarized by presenting the number (frequency) and percentage in each category.

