17.0 STUDY SCHEDULE

Table 4 Schedule of Assessments Group 1

Group 1: Subjects from Cohort 17 in the GBT440-001 study who have received GBT440 900mg per day for 4 months will continue receiving GBT440 900 mg per day for a further 2 months.

Assessments	Enrolment	Outpatient Treatment Period							
		1 a	15 +/-3 days g	30 +/-3 days	45 +/-3 days g	60 +/-3 days	67 +/-3 days	74 +/-5 days	88 end
Visit number	0	1		2		3	4	5	6
Informed consent	X	X							
Eligibility assessment	X	X							
Medical History	X								
Physical examination b	X		X	X	X				X
Weight	X		X	X	X	X			X
Vital signs	X	X	X	X	X	X			X
12 Lead ECG (single) c				X		X			X
Drug administration d		X				X			
Adverse events		X-----							-X
Urinalysis e	X		X		X				X
Urine microalbumin/creatinine	X								X
Haematology e	X		X	X	X				X
Serum biochemistry e	X		X	X	X				X
Coagulation e	X		X		X				X
Pregnancy test (females only)	X			X		X			X
Haemoglobin electrophoresis									X
PK samples (plasma and whole blood) f	X			X		X	X	X	X
Serum erythropoietin	X ^h			X		X			X
Exploratory plasma biomarkers	X ^h			X		X			X
Dense cells	X ^h			X		X			X
Carboxyhaemoglobin	X ^h								X
HbA1c	X ^h								X
NT-proBNP	X ^h								X
Concomitant medication diary	X-----								-X

Key

- a: Enrolment and visit 1 may be combined. On admission to the clinic the subjects will be asked whether they want to be considered for study GBT440-024. If the subject is interested in being enrolled on study GBT440-024 all consent activities will be completed before the samples/procedures for GBT440-001 or GBT440-024 are collected/Performed. Visit 0 (enrolment visit) is the last day of treatment in GBT440-001, which can be 6 days before Visit 1. If the last day of treatment in GBT440-001 (Day 118 or Day 60 for Cohort 17 and Cohort 15) – the enrolment visit is not being repeated as standalone visit.
- b: Complete physical examination on enrolment, a limited physical examination on all other days. Directed physical examinations will be performed as required.
- c: 12 lead ECG (single) will be performed within 30 minutes prior to dose
- d: GBT440 900 mg(three capsules) will be administered daily in the morning. On days when PK samples are drawn GBT 440 should be administered after an overnight fast.

During the dosing period subjects will be contacted every week in between out-patient visits to confirm GBT440 administration and subject well -being.

- e: Additional samples will be collected if clinically indicated

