- f: PK samples will be drawn pre dose. If the dose is increased to 1500 mg, please collect the following timepoints: pre dose, then 1-4 hours, 6-8 hours and 24 hours post dose on study visit days of Day 15 (± 3 days), Day 60 (± 3 days) and Days 90 (± 3 days) of receiving 1500 mg.g: Days 15 and 45 are only to be conducted if the dose is increased to 1500 mg.
- h: Can be omitted if measurements were collected in the past 7 days as part of the GBT440-001 study.

Table 5 Schedule of Assessments for Groups 2, 4 and 5

Groups 2: Subjects from Cohort 17 in the GBT440-001 study who have received placebo for 4 months will receive GBT440 900mg per day for 6 months

Group 4: Subjects from Cohort 15 in the GBT440-001 study who have received placebo for 2 months will receive GBT440 900 mg per day for 6 months

Group 5: Subjects with SCD from Cohorts 7, 11, 12, 14, 16 or 17 in the GBT440-001 study will receive GBT440 900 mg per day for 6 months

Assessments	Enrolment a	Baseline for Cohort 7,11,12,14, 16 or 17 (within 7 days of Day 1)	Outpatient Treatment Period											
			1 +/-3 days a	15 +/-3 days	30 +/-3 days	45 +/-3 days	60 +/-3 days	90 +/-3 days	120+/-3 days	150+/-3 days	180 +/-3 days	187+/-3 days	194 +/-5 days	208 End
Day number	Last treatment day GBT440-001 (+6 days) Cohorts 15 and 17													
Visit number	0		1	2	3	4	5	6	7	8	9	10	11	12
Informed consent	X	X												
Eligibility assessment	X	X												
Medical History	X	X												
Physical examination b	X	X		X	X		X	X	X	X	X			X
Weight	X	X		X	X	X	X	X	X	X	X			X
Vital signs	X	X	X	X	X	X	X	X	X	X	X			X
12 Lead ECG (single) c	X	X			X		X	X	X	X	X			
Drug administration d				X-----							X			
Adverse events				X-----										X
Urinalysis e	X	X						X	X	X	X			X
Urine microalbumin/creatinine	X	X						X			X			
Haematology e	X	X		X	X	X	-	X	X	X	X			X
Serum biochemistry e	X	X		X	X	X	X	X	X	X	X			X
Coagulation e	X	X		X		X		X	X	X	X			X
Pregnancy test (females only)	X	X			X		X	X	X	X	X			X
Haemoglobin electrophoresis		X						X			X			X
PK samples (plasma and whole blood) f	X			X	X		X	X	X	X	X	X	X	X
Serum erythropoietin	X ^h	X			X		X	X	X	X	X			X
Exploratory plasma biomarkers	X ^h	X			X		X	X	X	X	X			X

Assessments	Enrolment a		Outpatient Treatment Period											
			1 +/-3 days	15 +/-3 days	30 +/-3 days	45 +/-3 days	60 +/-3 days	90 +/-3 days	120+/-3 days	150+/-3 days	180 +/-3 days	187+/-3 days	194 +/-5 days	208 End

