Day number	Last treatment day GBT440-001 (+6 days) Cohorts 15 and 17	Baseline for Cohort 7,11,12,14, 16 or 17 (within 7 days of Day 1)	a											
Dense cells	X ^h	X			X		X	X	X	X	X			X
Carboxyhaemoglobin	X ^h	X						X			X			X
HbA1c	X	X						X			X			X
NT-proBNP	X ^h	X						X			X			X
Concomitant medication diary		X	X-----											X

Key

Note: Visit 0 is the last treatment day for subjects in GBT-440-001 (Day 118 for Cohort 17 and Day 60 for Cohort 15)

- a: Enrolment and visit 1 may be combined. On admission to the clinic the subjects will be asked whether they want to be considered for study GBT440-024. If the subject is interested in being enrolled on study GBT440-024 all consent activities will be completed before the samples/procedures for GBT440-001 or GBT440-024 are collected/Performed. Visit 0 (enrolment visit) is the last day of treatment in GBT440-001, which can be 6 days before Visit 1. If the last day of treatment in GBT440-001 (Day 118 or Day 60 for Cohort 17 and Cohort 15) – the enrolment visit is not being repeated as standalone visit.
- b: Complete physical examination on enrolment, a limited physical examination on all other days. Directed physical examinations will be performed as required.
- c: 12 lead ECG (single) will be performed within 30 minutes prior to dose
- d: GBT440 900mg(three capsules) for Group 2 and GBT 440 600mg (2 capsules) for Group 4 and GBT440 900 mg (3 capsules) for Group 5 will be administered daily in the morning. On days when PK samples are drawn GBT 440 should be administered after an overnight fast.
- During the dosing period, subjects will be contacted every week in between outpatient visits to confirm GBT440 administration and subject well being.
- e: Additional samples will be collected if clinically indicated
- f: PK samples will be drawn pre dose. If the dose is increased to 1500 mg, please collect the following timepoints: pre dose, then 1-4 hours, 6-8 hours and 24 hours post dose on study visit days of Day 15 (±3 days), Day 60 (±3 days) and Days 90 (±3 days) of receiving 1500 mg.
- h: Can be omitted if measurements were collected in the past 7 days as part of the GBT440-001 study.

Table 6 Schedule of Assessments Group 3

Group 3: Subjects from Cohort 15 in the GBT440-001 study who have received GBT440 600 mg per day for 2 months will continue receiving GBT440 600 mg per day for a further 4 months (the dose may be increased if the subject tolerated 600 mg in GBT440-001).

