Assessments	Enrolment	Outpatient Treatment Period									
		Last treatment day GBT440-001 (+6 days) a	1 +/-3 days a	30 +/-3 days	45 +/-3 days ^g	60 +/-3 days	90 +/-3 days	120+/-3 days	127 +/-3 days	134+/-5 days	148 End
Visit number	0	1	2		3	4	5	6	7	8	
Informed consent	X	X									
Eligibility assessment	X	X									
Medical History	X										
Physical examination b	X		X	X	X	X	X				X
Weight	X		X	X	X	X	X				X
Vital signs	X		X	X	X	X	X				X
12 Lead ECG (single) c	X		X		X	X	X				X
Drug administration d	X-----					X-----					
Adverse events	X-----										X
Urinalysis e	X			X		X	X				X
Urine microalbumin/creatinine	X						X				X
Haematology e	X		X	X	X	X	X				X
Serum biochemistry e	X		X	X	X	X	X				X
Coagulation e	X			X		X	X				X
Pregnancy test (females only)	X		X		X	X	X				X
Haemoglobin electrophoresis					X	X					X
PK samples (plasma and whole blood) f	X		X		X	X	X	X	X	X	X
Serum erythropoietin	X ^g		X		X	X	X	X			X
Exploratory plasma biomarkers	X ^g		X		X	X	X				X
Dense cells	X ^g		X		X	X	X				X
Carboxyhaemoglobin	X ^g				X						X
HbA1c	X ^g					X					X
NT-proBNP	X ^g					X					X
Modified SCD severity questionnaire	X		X		X	X	X	X			X
Concomitant medication diary	X-----										-X

Key

- a: Enrolment and visit 1 may be combined. On admission to the clinic the subjects will be asked whether they want to be considered for study GBT440-024. If the subject is interested in being enrolled on study GBT440-024 all consent activities will be completed before the samples/procedures for GBT440-001 or GBT440-024 are collected/Performed. Visit 0 (enrolment visit) is the last day of treatment in GBT440-001, which can be 6 days before Visit 1. If the last day of treatment in GBT440-001 (Day 118 or Day 60 for Cohort 17 and Cohort 15) – the enrolment visit is not being repeated as standalone visit.
- b: Complete physical examination on enrolment, a limited physical examination on all other days. Directed physical examinations will be performed as required.
- c: 12 lead ECG (single) will be performed within 30 minutes prior to dose
- d: GBT440 600mg (two capsules) will be administered daily in the morning. On days when PK samples are drawn GBT 440 should be administered after an overnight fast.

During the dosing period, subjects will be contacted every week in between outpatient visits to confirm GBT440 administration and subject well-being.

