- e: PK samples will be drawn pre dose. . If the dose is increased to 1500 mg, please collect the following timepoints: pre dose, then 1-4 hours, 6-8 hours and 24 hours post dose on study visit days of Day 15 (± 3 days), Day 60 (± 3 days) and Days 90 (± 3 days) of receiving 1500 mg.
- f: Days 45 are only to be conducted if the dose is increased to 1500 mg.
- g: Can be omitted if measurements were collected in the past 7 days as part of the GBT440-001 study.

[figure not shown]

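### Section 12.4 gives the haemolysis markers no common analysis baseline and no split by on-drug or off-drug entry, so rows pooled on study day could misstate the change on GBT440

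*Combined protocol and SAP*

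**What the plan says.** Section 12.4 is a single sentence: "Haemolysis and Disease related assessments will be listed and summarised at each time point using appropriate descriptive statistics". It names no baseline, change score, treatment group, dose or entry status, and the synopsis adds none. Section 12.2 defines one PD population for every PD summary. Section 12.3, by contrast, names two by-variables for PK: dose and study day. Section 12.0 states that "Details of all planned analyses will be specified in a separate statistical analysis plan"; the document as supplied contains no text from that plan.

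Treatment status at entry differs by group (Sections 7.1 and 8.6):

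- **Group 1** is on drug. The Table 4 heading describes subjects "who have received GBT440 900mg per day for 4 months will continue receiving GBT440 900 mg per day for a further 2 months".
- **Group 3** is on drug, after two months at 600 mg.
- **Groups 2 and 4** come from placebo.
- **Group 5** is off study, and therefore off drug.

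For continuing subjects, footnote a of Tables 4 and 6 says: "Visit 0 (enrolment visit) is the last day of treatment in GBT440-001, which can be 6 days before Visit 1". For % dense cells, the entry sample may come from the parent study: "Can be omitted if measurements were collected in the past 7 days as part of the GBT440-001 study" (Table 4 footnote h, Table 6 key item g).

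The visit grid also differs. Table 4 footnote g says "Days 15 and 45 are only to be conducted if the dose is increased to 1500 mg", and the Table 6 key says "Days 45 are only to be conducted if the dose is increased to 1500 mg". Table 5 schedules both days for everyone in Groups 2, 4 and 5. It has a baseline column, but only for the off-study cohorts that form Group 5.

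**The concern.** Section 6.2 makes the effect on haemolysis biomarkers a secondary objective, and these descriptive tables are the only summary planned for it. Study day is the only axis named, but it does not measure the same thing in every group. For Groups 2, 4 and 5 the entry row is a value without drug. For Groups 1 and 3 it already contains the response to two or four months of GBT440. A difference between the entry row and a later row, taken over everyone, would then average a treatment response with a continuation response. Neither would be visible on its own.

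The rows also change membership, because dosing stops at different days in different groups. Differences between later rows and the entry row partly reflect who is still being dosed.

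**Working it through.** The plan states no effect size, SD or group sizes, so there is no figure of its own to reproduce.

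**Exposure behind a Day 30 value.** The last parent-study treatment days come from the Table 5 key: "Note: Visit 0 is the last treatment day for subjects in GBT-440-001 (Day 118 for Cohort 17 and Day 60 for Cohort 15". Assume a sample before that morning's dose, so 29 dosing days in this study, and ignore any gap between the studies (at most 7 days under inclusion criterion 1).

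- Group 1: 118 + 29 = 147 dosing days
- Group 3: 60 + 29 = 89
- Groups 2, 4 and 5: 29 in the current course

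Haematology and serum biochemistry are scheduled at Day 30 in all three tables, so one pooled row would hold all three exposures.

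**Entry-to-Day-30 difference in a pooled row.** Let D be the mean change in the off-drug starters, f the share of subjects on drug at entry, and r the continuing subjects' mean further change as a fraction of D. With the same subjects in both rows:

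pooled difference = (1-f) x D + f x (r x D) = D x [(1-f) + f x r]

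This is a weighted mean of changes, so it does not depend on the groups' starting levels. Neither f nor r is in the documents. Section 5.2.1 reports that two Cohort 17 subjects had enrolled by 03 August 2016, without their allocation. Taking N=16, the enrolment cap, the multiples of D are:

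| f | r=0 | r=0.5 | r=1 | r=1.5 |
|---|---|---|---|---|
| 0 | 1.00 | 1.00 | 1.00 | 1.00 |
| 2/16 | 0.875 | 0.9375 | 1.00 | 1.0625 |
| 4/16 | 0.75 | 0.875 | 1.00 | 1.125 |
| 8/16 | 0.50 | 0.75 | 1.00 | 1.25 |

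For example, at f=4/16 and r=0.5: 0.75 + 0.25 x 0.5 = 0.875. At f=8/16 and r=1.5: 0.50 + 0.50 x 1.5 = 1.25.

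**Which r is plausible.** Section 5.3 reports improvement by 28 days and an initial impression, from blinded data, that it is sustained over 90 days. That points to a small r. Section 5.3.1 reports no plateau in the relation between blood level and haemolysis, and Section 8.2.1 allows dose increases after at least 28 days of dosing. Section 5.3.1 words that as prior dosing, so continuing subjects could titrate soon after entry, while new starters would reach the condition only around Day 30. That points to a larger r.

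**Row membership.** On-treatment rows end at Day 60 in Group 1, Day 120 in Group 3 and Day 180 in the others. With n1 and n3 subjects in Groups 1 and 3, the on-treatment count is at most 16 - n1 at Days 90 to 120 and 16 - n1 - n3 at Days 150 to 180. If n1=2 and n3=2, that is 14 and then 12.

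**Post-treatment visits.** Group 1's Day 88 is 88 - 60 = 28 days after dosing ends and lies next to the on-treatment Day 90 of Tables 5 and 6. Group 3's Day 148 is 148 - 120 = 28 days after dosing ends and lies next to Day 150 of Table 5. A visit window that merged them would mix off-drug and on-drug values.

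**The case against.** The strongest objection is that pooling is not planned anywhere. Section 12.0 defers detail to a separate plan, and the protocol is built on five groups and three schedules that already separate Group 1, Group 3 and Groups 2, 4 and 5. A time point could be read as one within a schedule. This stands: a reader might infer that the trial will pool these rows, and the documents do not say so. Pooling is only what the sentence gives if applied literally to a single PD population, and Section 12.3 shows that the authors name by-variables elsewhere.

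A second objection also stands. A reader might infer that pooling must understate the effect. That needs f>0 and r<1. The number of continuing subjects may be zero: Section 5.3 says several Cohort 17 subjects had finished dosing and could not take part. Early titration could put r at or above 1.

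Third, a reader might infer that the different genotypes in Groups 3 and 4 (Cohort 15) could shrink, inflate or even reverse late rows by a calculable amount. The documents give no marker levels by genotype, and Section 5.2.1 has only seven Cohort 15 subjects due for 60 days of dosing. No size can be put on this.

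The existence of a baseline visit for Group 5 does not answer the point, because it is not an analysis baseline for all groups.

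**Conclusion.** The point holds as a gap with a conditional consequence. Section 12.4 does not define a common analysis baseline or a split by entry status, and the entry value that this study collects for Groups 1 and 3 is an on-drug value. This goes beyond missing detail: even a table of change from the entry visit would not show the treatment response in those two groups.

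The size rests on assumed values of f and r and on pooling by study day. Under those conditions the pooled Day 30 difference is half of the starters' change at f=8/16 with r=0, equal to it at f=0 or r=1, and above it if r>1. The changing row membership follows from the schedules whenever Group 1 or Group 3 has subjects.

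The consequence is limited. The primary objective is safety, and the individual values will be listed, so the response could be recovered by hand. The point is worth settling before the analysis plan is final.

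**What to change.** State in Section 12.4 and in the separate analysis plan:

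1. **Baseline** is the last value before the current continuous GBT440 course (allowing the gap of up to 7 days in inclusion criterion 1). Take it from GBT440-001 for Groups 1 and 3, and from this study's pre-dose visit for Groups 2, 4 and 5. Flag Group 5 subjects with earlier GBT440 exposure.
2. **Summaries** of values and of change from that baseline are given separately for Group 1, Group 3, and Groups 2, 4 and 5, matching Tables 4, 6 and 5. Each row shows n, time since the start of the course and current dose. This keeps subjects who enter at 600 mg and 900 mg on drug apart.
3. **Post-treatment visits** (such as Day 88 in Group 1, Day 148 in Group 3 and Day 208 in the others) stand in rows of their own.

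The cost is wording plus reuse of parent-study values, with no new samples or visits. Figure 1 already shows haemoglobin as change from baseline. The price is very small cells: the Group 1 table might hold two subjects or none. Change from baseline removes differences in starting level, but not differences in response by dose or genotype, so the listings remain necessary.

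Separately, the Group 4 dose differs between the Table 5 heading (900 mg) and Table 5 footnote d (600 mg); the two must be reconciled.

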12.5 Safety Data Analysis

Individual and summary blood pressures, heart rate, body temperature, respiratory rate, ECG parameters and clinical laboratory data (haematology, serum biochemistry and coagulation) will be presented in tabular form with appropriate descriptive statistics. Adverse events will be tabulated and summarized.

13.0 STUDY REPORT

A clinical study report, compliant with the requirements of ICH E3, will be prepared by Quintiles.

14.0 REGULATORY AND ETHICAL ISSUES

14.1 Regulatory and Ethics Review and Approval

The study will be submitted for to the Medicines and Healthcare products Regulatory Agency (MHRA-UK) for review and approval and to an Ethics Committee for ethical review and approval.

14.2 Informed Consent

Informed consent will be given freely after the subject has been informed of the nature, significance, implications and risks of the trial; and consent is evidenced in writing, dated and signed, or otherwise marked, by that person so as to indicate his/her consent, prior to the start of the study. The nature of the informed consent will comply with the current version of the Declaration of Helsinki, the current requirements of GCP (Committee for Proprietary Medicinal Products/ICH/135/95 and local regulation (The requirements are set out in Schedule 1 of Statutory Instrument 1031 and amendments) which ever provides the greater subject protection.

14.3 Indemnity and Compensation

In accordance with Statutory Instrument 1031 and amendments section 15 (5i, j) and the EU Clinical Trials Directive 2000/20/EC Article 3 (2f), provision is to be made for:

- The indemnity or compensation in the event of injury or death attributable to the clinical trial; and
- Insurance or indemnity to cover the liability of the Investigator or Sponsor.

Therefore the Sponsor Global Blood Therapeutics Inc will indemnify the Investigators, The BRC Clinical Research facility (KCL and GSTT) from all and any claims arising out of this study except for their negligence or malpractice and providing that the study is conducted according to the standards established by the protocol.

In the event that it can be demonstrated that a subject suffers any significant deterioration in health or well-being or any harmful susceptibility or toxicity as a direct result of their participation in this study then Global Blood Therapeutics, Inc will agree to abide by the current ABPI and FDA with regard to compensation payable to the subject. The amount of compensation will be calculated by reference to the level of damages commonly awarded in law for UK for similar injuries at the time when such injury occurred.

The Investigators, The BRC Clinical Research facility (KCL and GSTT) declare to having insurance cover for the malpractice and/or negligence of their employees and agents.

15.0 STUDY MANAGEMENT

15.1 Quality Assurance and Quality Control

In accordance with the guideline for ICH GCP, the Sponsor has responsibility for implementing and maintaining quality assurance and quality control systems, and the ultimate responsibility for the quality integrity of the trial data resides with the Sponsor.

15.2 Protocol Adherence

The protocol must be read thoroughly and the instructions followed exactly. Any deviations should be agreed by both the Sponsor and the Investigator, with the appropriate written and approved protocol amendments made to reflect the changes agreed upon. Where the deviation occurs for the well-being of the subject, the Sponsor must be informed of the action agreed upon.

15.3 Documents Necessary for Initiation of Study

The following documents will be available prior to the first administration of the drug to the first subject:

- Regulatory authorisation;
- Copy of current Investigator's Brochure;
- Risk assessment report;
- Completed and signed investigator agreement/contract;
- Signed original of the final protocol;
- Ethics Committee approval;
- Copy of the constitution of the Research Ethics Committee;
- A list of members of the Ethics Committee;
- A copy of the consent form and subject information to be used;
- The curriculum vitae of all Investigators;
- The Qualified Person's certification for the release of each batch of IMP;
- A technical agreement between the Sponsor and The Investigational Site defining the responsibilities of the Sponsor, The Investigational Site and Quintiles Ltd. and any third parties significantly involved in the supply chain of the IMP, where applicable;

- The product specification file, where applicable; and

A list of laboratory reference range values for parameters measured in the study.

